#### 7.13.2 Timing

Adverse event assessment and documentation will occur at every study visit from screening throughout the study. On the day of treatment administration, a subject's medical complaint will be considered to be a treatment-emergent adverse event if the event occurs any time after the first exposure of investigational product at the beginning of the catheterization for the infusion of CAP-1002. For subjects receiving usual care, an event is considered treatment-emergent if it occurs on or after 9:00 am (in the subject's time zone) on Day 0.

#### 7.13.3 Severity

The Investigator will make an assessment of intensity for each AE and SAE reported during the study. The assessment will be based on the Investigator's clinical judgment. The intensity of each AE and SAE will be assigned to one of the following categories:

**Mild:** An event that is easily tolerated by the subject, causing minimal discomfort and not interfering with everyday activities.

**Moderate:** An event that is sufficiently discomforting to interfere with normal everyday activities.

**Severe:** An event that prevents normal everyday activities.

An AE that is assessed as severe will not be confused with an SAE. Severity is a category utilized for rating the intensity of an event; and both AEs and SAEs can be assessed as severe. An event is described as 'serious' when it meets one of the pre-defined outcomes as described in the Section 7.13.8 Serious Adverse Events.

#### 7.13.4 Relationship

The Investigator is obligated to assess the relationship between study therapy and the occurrence of each AE/SAE. The Investigator will use clinical judgment to determine if there is a reasonable possibility that the pharmacological action of the study agent, or the infusion procedure itself, was responsible for the AE/SAE being reported. Alternative causes such as natural history of the underlying diseases, concomitant therapy, other risk factors, and the temporal relationship of the event to the study agent will be considered and investigated. The Investigator will also consult the Investigator's Brochure and/or Product Information, for marketed products, in the determination of his/her assessment.

All AE/SAE that occur during the course of the clinical study will be evaluated. For each AE/SAE, the investigator will make a determination of relatedness to the investigational product and, separately, assess relatedness to the procedure. Each will be defined according to one of the following categories:

**Definite:** The AE/SAE is clearly related to the investigational product or procedure.

**Probable:** The AE/SAE is likely related to the investigational product or procedure.

**Possible:** The AE/SAE may be related to the investigational product or procedure. All AEs and SAEs that occur within 24 hours of intervention will, because of the temporal relationship, be considered as at least possibly related to the procedure and will be reported to the DSMB.

**Unlikely:** The AE/SAE is doubtfully related to the investigational product or procedure.

**Unrelated:** The AE/SAE is clearly NOT related to the investigational product or procedure.

There may be situations when an SAE has occurred and the Investigator has minimal information to include in the initial report. However, it is very important that the Investigator make an assessment of causality

#### 7.13.5 Expectedness

The following adverse events are considered to be expected as a result of the catheterization and infusion procedure:

- Some premature ventricular contractions, non-sustained ventricular tachycardia (<30 sec duration)
- Hypotension (Systolic Blood Pressure <80mmHg) and/or bradycardia (Heart Rate <50 beats/min) that responds rapidly to fluid, atropine and possibly vasopressor administration, if required
- Reduction of coronary blood flow, TIMI flow grade I or II, persisting <3 min after balloon deflation, during cell infusion
- Angina, duration <10 min during cell infusion
- ST elevations, duration <3min during cell infusion, troponin elevations above the 99th percentile but not more than 3x, at any time during the first 24 hours after cell infusion
- Dissection of one or more of the infused arteries
- Bleeding, bruising and/or hematoma formation at the site of vascular access for the cell infusion procedure, at any time within the first 24 hours after cell infusion

All adverse events expected or otherwise, should be reported in the subject data. Serious Adverse Events (SAEs) should be reported to the Sponsor within 24 hours of the site learning of the event.

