## 1.7 Potential Risks and Benefits

Risks associated with administration of the study agent are primarily related to placing a guidewire down the coronary arteries in order to position the infusion catheter. The risk of coronary dissection is estimated to be less than 1% in this setting (Janssens, Dubois et al. 2006, Schachinger, Erbs et al. 2006, Assmus, Leistner et al. 2014) **CCI**

Other risks of the infusion procedure include those risks that are possible with diagnostic coronary angiography. These include risks related to infection, bleeding, hypotension, pain and hematoma at the arterial puncture site (0.4%), arrhythmia (0.38%), sensitivity or allergy to radiographic contrast (0.37%), exposure to radiation, thromboembolism (0.07%), contrast induced nephropathy, myocardial ischemia or infarction (0.05%). Overall, the risk of any complication is approximately 1.4%, and for death is less than 0.1% (Noto, Johnson et al. 1991). These reported rates of complication include subjects with significant cardiac disease and other comorbidities.

CAP-1002 CDCs are grown from donated human myocardial tissue and **CCI**

CCI

Contrast dye is used for the angiography and MRI. There is a small risk of an allergic reaction causing rash, itching, hives or wheezing, but very rarely (0.07%) are reactions severe (Dillman, Ellis et al. 2007). Subjects will be assessed for any previous allergic reaction to contrast prior to procedures utilizing dye. Antihistamine and steroid may be used to pre-medicate subjects who have a history of sensitivity or allergy, according to the hospital's usual practice. There is also a small (5%) possibility of developing abnormal function of the kidneys (Katzberg and Newhouse 2010). This abnormal kidney function is usually temporary and less likely if there is no underlying kidney function abnormality. Additionally, the kidney abnormality is generally resolved by the natural elimination of the contrast dye from the subject's system. Creatinine clearance or GFR will be assessed prior to tests requiring contrast. Contrast solution and timing of the test may be adjusted in subjects with impairment of kidney function. Subjects will be closely monitored for any signs of allergic reaction or decrease in renal function as well as any other side effects.

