#### 6.10.2 Infusion Procedure Stopping Criteria

The operator will continuously monitor for the following Stopping Criteria. If any Stopping Criteria are met, the infusing Investigator must stop the infusion and assess for clinical significance. The infusing Investigator may continue with the infusion if, based on the infusing Investigator's medical judgement and clinical context, no additional risk is presented to the subject.

1. Development of TIMI flow 0-2 or TIMI myocardial perfusion grade (TMPG) 0-2 persisting for  $>3$  minutes after a cycle of infusion, despite administration of intracoronary vasodilators;
2. Sustained hypotension unresponsive to fluids and/or atropine/vasopressor administration;
3. Evidence of cerebrovascular accident;
4. Evidence of cardiac tamponade;
5. Hemopericardium requiring pericardiocentesis;

6. Sustained VT/VF that requires cardioversion/defibrillation or administration of an antiarrhythmic;
7. Evidence of thrombus in the aorta that was not previously seen;
8. Suspected or confirmed aortic dissection;
9. Suspected or confirmed coronary dissection;
10. Other evidence of acute myocardial infarction;
11. Acute onset of rigors (symptoms indicative of acute sensitivity or infection).

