### 7.13.8.2 Reporting Serious Adverse Events

All SAEs, including any fatal or life-threatening event, must be reported within 24 hours from the time the Investigator is made aware of the event. If the Investigator does not have all information regarding an SAE, he/she will not wait to receive additional information before recording the event in the data system and completing as much information known at the time of the submission.

To report the event, an SAE form must be completed and submitted to the data management group within the appropriate reporting timelines as further described in the study manual. Additionally, the Medical Monitor should be contacted and informed of the event, preferably by fax, as follows:

United BioSource Corporation  
[contact]  
[contact]  
Email: [[contact]](mailto:[contact])

The Medical Monitor will review all information provided and contact the Investigator for additional information, as necessary.

Per ICH E2A and 21 CFR 312, regulatory agencies will be notified by the Sponsor by telephone or fax of any unexpected, SAE potentially associated with treatment as soon as possible, but in no event later than 15 calendar days after the Sponsor's initial receipt of the information; fatal or life-threatening unexpected SAEs associated with treatment will be reported to regulators within 7 calendar days. Follow-up information will be provided as required.

All AEs and SAEs documented at a previous visit/contact that are designated as ongoing will be reviewed at subsequent visits/contacts.

All AEs (including SAEs) will be followed until resolution, until no further changes in the event are expected (i.e. the point at which a subject experiencing an adverse event is treated successfully and stabilized even though they may continue to experience sequelae) as confirmed by the Investigator, until the subject is lost to follow-up, or until the subject's 12 Month Visit. Subjects will be contacted by phone annually through year 5 post-infusion to assess for acute or planned procedure and/or admission for cardiac cause as well as survival. If a subject dies during participation in the study or during a recognized follow-up period, the Medical Monitor will be provided with a copy of any post-mortem findings, including histopathology.

New or updated information will be recorded by modifying the AE forms in the data system.

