The Investigator will promptly report all SAEs within the timeframes specified in this protocol. The Investigator will comply with the applicable local regulatory requirements related to reporting of SAEs to his or her Institutional Review Board (IRB) or Independent Ethics Committee (IEC).

This protocol is being filed under an Investigational New Drug (IND) application with the FDA in the US as well as with other international regulatory agencies. A given SAE may qualify for an Expedited Safety Report (ESR) if the SAE is both attributable to study therapy and unexpected. In this case, all Investigators participating in the study will receive the ESR. The purpose of the ESR is to fulfill specific regulatory and Good Clinical Practice (GCP) requirements regarding the product under investigation.

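### Coronary dissection of any severity is listed as expected, so as written a serious case triggers no expedited notice to regulators or other investigators

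*Protocol*

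**What the plan says.** Protocol 7.13.5 opens its list with "The following adverse events are considered to be expected as a result of the catheterization and infusion procedure". Most cardiac items carry a bound, for example "Angina, duration <10 min during cell infusion" and "Reduction of coronary blood flow, TIMI flow grade I or II, persisting <3 min after balloon deflation, during cell infusion". One item reads only "Dissection of one or more of the infused arteries".

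Two other sections deal with the same event. Section 6.10.2, item 9, names "Suspected or confirmed coronary dissection" among the criteria at which the operator must stop the infusion and assess; the operator may then continue if judging that no additional risk arises. Section 1.7 states: "The risk of coronary dissection is estimated to be less than 1% in this setting".

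Section 7.13.8.2 makes expedited reporting depend on expectedness. The sponsor notifies regulators of "any unexpected, SAE potentially associated with treatment as soon as possible, but in no event later than 15 calendar days", with 7 calendar days for fatal or life-threatening unexpected cases. An SAE may qualify for the Expedited Safety Report, which goes to every participating investigator, "if the SAE is both attributable to study therapy and unexpected".

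**The concern.** An unqualified entry in the expected list puts a serious dissection in the same reporting class as brief angina or bruising at the puncture site. The operator has to stop and assess for it, and the protocol regards it as rare, yet its seriousness has no effect on whether it is expedited.

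What is at stake is who hears about it, and by what formal route. This is the first use of the product in DMD and the first trial of it not confined to adults (section 1). Each treated subject is to have three coronary territories infused in one procedure. The Expedited Safety Report is the only expedited notice to other investigators that the protocol describes. The DSMB reports to the sponsor and has no contact with the clinical centers (10.2).

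**Working it through.** **1. The expected list against the stopping criteria**

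| Event | Expected under 7.13.5 | Stopping criterion in 6.10.2 |
|---|---|---|
| Reduced coronary flow | Grade I or II, under 3 min | Item 1: beyond 3 min despite vasodilators |
| Hypotension | Responds rapidly to treatment | Item 2: sustained and unresponsive |
| Ventricular tachycardia | Non-sustained, under 30 s | Item 6: sustained VT/VF needing intervention |
| ST elevation; troponin | Under 3 min; not more than 3x | Item 10: other evidence of acute MI |
| Angina | Under 10 min | No direct counterpart |
| Coronary dissection | Any, in one or more infused arteries | Item 9: suspected or confirmed |
| Access-site bleeding, bruising, hematoma | First 24 h, any severity | None |

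In the first four rows the expected form ends at or before the point where the stopping criterion begins. Only for dissection do the two overlap completely. The access-site item has a time limit but no severity limit.

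**2. The reporting chain for a serious dissection**

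- Serious: a dissection that prolongs the post-infusion stay, or is life-threatening, meets the SAE definition in 7.13.8.1.
- Related: 7.13.4 counts the infusion procedure when relationship to study therapy is judged, and deems any event within 24 hours at least possibly related to the procedure.
- Unexpected: 7.13.5 says it is not.

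The third condition fails, so neither the regulator reports nor the Expedited Safety Report is triggered. Nothing in 7.13.5 or 7.13.8.2 takes a serious dissection back out of the list.

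**3. How often this could arise**

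The risk below 1% is a literature figure given without numerator or denominator, so it cannot be reproduced. Taking 1% as the ceiling per infused subject, with n = 12 (the infusion target in 3.1) and independence between subjects:

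- Expected number: 12 x 0.01 = 0.12.
- P(at least one) = 1 - 0.99^12 = 0.1136, or 11.4%.
- P(two or more) = 1 - 0.99^12 - 12 x 0.01 x 0.99^11 = 0.0062, or 0.6%.
- At 0.5%, P(at least one) is 5.8%; at 0.1%, it is 1.2%.

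If the 1% were per artery (an assumption; 12 x 3 = 36 arteries, taken as independent), the expected number is 0.36 and P(at least one) = 1 - 0.99^36 = 30.4%.

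One case in 12 would be 8.3% (exact 90% CI 0.4% to 33.9%), still compatible with 1%. Two would be 16.7% (3.0% to 43.8%), which is not. These figures count dissections of any severity, so for a given risk they are upper bounds for serious ones.

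**The case against.** The strongest reply is that much of the safety reporting does not depend on expectedness:

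- Every SAE goes to the sponsor within 24 hours, and the Medical Monitor is to be informed (7.13.5, 7.13.8.2).
- The Medical Monitor or designee reviews it within one business day (7.13.9).
- Events within 24 hours of the intervention are reported to the DSMB (7.13.4).
- The CEC adjudicates serious and intervention-related events, meeting every 6 months or as needed (10.1).
- The DSMB reviews the 72-hour data of Group 1 before Group 2 opens (3.1).

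This stands. A reader might infer that an excess of dissections would come to light only at a periodic DSMB meeting; these provisions contradict that.

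A reader might also infer that restoring the reports would warn other sites before their next infusion. The documents do not support this. Infusions may be three days apart, the regulator reports allow 7 or 15 days, and the Expedited Safety Report has no stated deadline. The stagger itself is there to detect acute complications.

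Third, expected in 7.13.5 means recognized as a result of the procedure, not frequent. A known rare complication can be listed and still be a reason to pause, and item 9 lets the operator continue after assessment. It is not a study stopping rule; those are in the DSMB Charter. So the sections are not in strict logical conflict. What remains is that the listing has no limit and no text says how it applies to a serious case.

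Finally, text directly after the risk figure in 1.7 is redacted and may explain the listing.

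**Conclusion.** The point holds for expedited notice to regulators and other investigators, and only there. As the protocol is written, a serious dissection of an infused artery does not meet the condition for either. The sponsor could still choose to treat a severe case as unexpected, but the text does not provide for it.

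It is tempting to say that a fatal dissection would go unreported to regulators. The documents leave that open. Death, acute MI and tamponade are not on the expected list, and nothing says that such an outcome becomes expected because dissection is listed. On the other hand, 7.13.1 asks for the diagnosis to be recorded rather than the signs and symptoms, which could bring the event under the listed term.

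The size is modest: most likely no dissection in 12 infused subjects, and an 11.4% chance of at least one of any severity at the stated ceiling. This takes the 1% as per subject. The conclusion also assumes that 7.13.5 governs expectedness for these reports; the protocol does not say whether expectedness for the product is judged from another document. The change is still worth making, because a small wording change closes the gap.

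**What to change.** Add one sentence to 7.13.5: any dissection of an infused artery, or any access-site bleed, that meets an SAE criterion is treated as unexpected for the reports in 7.13.8.2. In the same amendment, reconcile sections 1.7, 6.10.2 (item 9), 7.13.5 and 7.13.8.2, and state how a fatal or life-threatening outcome of a listed event is classified.

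This changes reporting classification only. The stopping criteria, the operator's discretion to continue and the care of subjects are untouched. The cost is a short amendment and probably zero or one extra expedited report for dissection.

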#### 7.13.6 Clinical Significance

An abnormal lab value or test result should be deemed clinically significant if either of the following conditions is met:

- The abnormality suggests a disease and/or organ toxicity that is new or has worsened from baseline.
- The abnormality is of a degree that requires additional active management, e.g., change of dose, discontinuation of a drug, close observation, more frequent follow-up assessments, or further diagnostic investigation.

A qualified physician at the investigative site, either the Investigator or a Sub-Investigator, will review all study-related laboratory and other test results. The reviewing Investigator will use his/her medical judgment to classify and document any results that are outside of the normal results range. The Investigator will indicate whether each abnormal result is clinically significant (CS) or not clinically significant (NCS) on the source document and case report form.

Once the Investigator deems an abnormal value to be clinically significant (CS), he or she will determine whether there is a clinical exam finding or symptom (new or pre-existing) that explains the abnormal value. A progress note summarizing the findings, including the reason(s) why the results are deemed CS will be written to provide documentation for an adverse event report. If the Investigator is able to provide a differential diagnosis for the CS result, he or she should describe the AE accordingly, e.g., urinary tract infection or suspected anemia. In the absence of an associated clinical sign or symptom, and if only a single value is deemed CS, list the abnormal value itself as the AE, e.g., elevated potassium or decreased calcium. As more information about the abnormal value is known that provides a diagnosis, the AE should be updated in the electronic data system to reflect the diagnosis.

#### 7.13.7 Clinical Laboratory Adverse Events

Abnormal laboratory findings (e.g. clinical chemistry, hematology, and urinalysis) that are judged by the Investigator as clinically significant (CS) will be documented as described in Section 7.13.1 and will be recorded as AEs or SAEs if they meet the definition of an AE as defined in Section 7.13.1 or SAE, as defined in Section 7.13.8.

Clinically significant abnormal laboratory findings that are detected during the study or are present at screening and significantly worsen following the start of the study will be reported as AEs or SAEs. However, clinically significant abnormal laboratory findings that are associated with the disease being studied, unless judged by the Investigator as more severe than expected for the subject's condition, or that are present or detected at the start of the study but do not worsen, will not be reported as AEs or SAEs.

The Investigator will exercise medical judgment in deciding whether abnormal laboratory values are clinically significant.

## 7.13.8 Serious Adverse Events

### 7.13.8.1 Definition

A serious adverse event (SAE) is defined by federal regulation as any AE occurring at any dose that results in any of the following outcomes: death, life-threatening AE, hospitalization or prolongation of existing hospitalization, a persistent or significant disability/incapacity, or a congenital anomaly/birth defect.

Important medical events that may not result in death, be life threatening, or require hospitalization may be considered an SAE when, based upon appropriate medical judgment, they may jeopardize the subject and may require medical or surgical intervention to prevent one of the outcomes listed in this definition. Examples of such medical events include allergic bronchospasm requiring intensive treatment in an emergency room or at home, blood dyscrasias or convulsions that do not result in inpatient hospitalization, or the development of drug dependency or drug abuse.

Complications that occur during hospitalization are AEs. If a complication prolongs hospitalization or fulfills any other serious criteria, the event is serious. Hospitalization for elective treatment of a pre-existing condition that did not worsen from baseline is not considered to be an AE.

The term disability means a substantial disruption of a person's ability to conduct normal life functions. This definition is not intended to include experiences of relatively minor medical significance such as uncomplicated headache, nausea, vomiting, diarrhea, influenza, accidental trauma (i.e., sprained ankle) that may interfere or prevent everyday life functions but do not constitute a substantial disruption.

